##### **4.4.1 Permitted Therapy**

Patients are permitted to use the following therapies during the study:

- *Progesterone only injectable or implantable contraceptives*

*Of note, a decrease in glucose tolerance has been observed in some patients treated with medroxyprogesterone acetate contraceptive injection treatment.*

*Medroxyprogesterone acetate injection contraception should be used with caution, given the potential risk of worsening glycemic control.*

- Prophylactic anti-emetic and antidiarrheal medications
- Prophylactic or therapeutic anticoagulation therapy

Caution should be exercised in patients receiving warfarin (Coumadin®) as rucaparib can be an inhibitor of CYP2C9. Patients taking warfarin should have their INR monitored regularly per standard clinical practice.

- Inactivated vaccinations
- Bisphosphonates or denosumab
- Palliative radiotherapy (e.g., treatment of known bony metastases or symptomatic relief of pain) as outlined below:

After Cycle 2, palliative radiotherapy is permitted, provided it does not interfere with the assessment of tumor target lesions (e.g., the lesion to be irradiated must not be the only site of measurable disease). Rucaparib may be continued during palliative radiotherapy. Treatment with ipatasertib should be suspended for at least 7 days before and after the procedure. For single-day radiotherapy, the ipatasertib hold may be shorter, if approved in advance by the Medical Monitor.

Premedication with antihistamines, antipyretics, and/or analgesics may be administered at the discretion of the investigator.

In general, investigators should manage a patient's care with supportive therapies as clinically indicated, per local standard practice.

#### **4.4.2            Cautionary Therapy**

Use of concomitant corticosteroids with ipatasertib can increase risk of hyperglycemia. Patients who require use of systemic corticosteroids  $\geq 10$  mg of prednisone (or an equivalent dose of other corticosteroid) should hold ipatasertib during that time period to reduce risk of hyperglycemia.

##### **4.4.2.1            Medications Given with Precaution due to Effects Related to Cytochrome P450 Enzymes**

Co-administration of rucaparib can increase the systemic exposure of CYP1A2, CYP3A, CYP2C9, or CYP2C19 substrates, which may increase the risk of toxicity of these drugs. Adjust dosage of CYP1A2, CYP3A, CYP2C9, or CYP2C19 substrates, if clinically indicated. If co-administration with warfarin (a CYP2C9 substrate) cannot be avoided, consider increasing the frequency of INR monitoring.

In vitro data suggest that ipatasertib is metabolized by CYP3A and may be a time-dependent inhibitor of CYP3A4. A clinical drug-drug interaction study with midazolam (a sensitive CYP3A substrate) showed a 2.2-fold increase in midazolam exposures in presence of steady-state ipatasertib dosed at 600 mg QD. Therefore, sensitive CYP3A substrates with narrow therapeutic window should be avoided. Given that ipatasertib is primarily metabolized by CYP3A, there is a high potential for drug-drug interactions of ipatasertib with any medication that strongly inhibits or induces CYP3A.

Data from a clinical study showed that ipatasertib exposures were reduced by approximately 50% when co-administered with enzalutamide, a strong CYP3A inducer. Strong CYP3A inhibitors are expected to increase ipatasertib exposures. Therefore, the following drugs should be avoided while taking ipatasertib:

- Strong CYP3A4/5 inhibitors, such as, but not limited to, atazanavir, clarithromycin, indinavir, itraconazole, ketoconazole, nefazodone, nelfinavir, ritonavir, saquinavir, telithromycin, troleandomycin, and/or voriconazole
- Strong CYP3A4/5 inducers, such as, but not limited to, rifampin, carbamazepine, rifapentine, phenytoin, phenobarbital, and/or St. John's wort or hyperforin
- CYP3A4/5 substrates with a narrow therapeutic index.

Note: Chronic use of strong CYP3A inhibitors or inducers, or sensitive CYP3A substrates with a narrow therapeutic window that are deemed not permissible by the Medical Monitor are prohibited (see Section 4.4.3)

Patients who require short-term use of a strong CYP3A4/5 inhibitor or inducer or use of sensitive CYP3A substrates with a narrow therapeutic window for medical treatment (i.e., an alternative treatment cannot be used) must exercise caution and all study treatment should be temporarily held until at least 5 half-lives or 7 days, whichever is shorter, after the last dose of these drugs.

Patients are permitted to take moderate inhibitors of CYP3A4/5 with caution. Patients should be closely monitored. Refer to the following information for further guidance on CYP450-drug interactions and a list of common substrates, inhibitors, and inducers:

Drug Development and Drug Interactions: Table of Substrates, Inhibitors, and Inducers (U.S. FDA):

<http://www.fda.gov/Drugs/DevelopmentApprovalProcess/DevelopmentResources/DrugInteractionsLabeling/ucm093664.htm>

The above lists of medications are not comprehensive. The investigator should consult the prescribing information when determining whether a concomitant medication can be safely administered with study treatment. In addition, the investigator should contact the Medical Monitor if questions arise regarding medications not listed above.

For additional information on rucaparib pharmacokinetics and drug interactions please refer to Rucaparib Package Insert or Summary of Product Characteristics.

#### **4.4.2.2 Herbal Therapies**

Concomitant use of herbal therapies is not recommended because their pharmacokinetics, safety profiles, and potential drug-drug interactions are generally unknown. However, herbal therapies not intended for the treatment of cancer may be used during the study at the discretion of the investigator. Herbal therapies that require caution or are prohibited due to CYP interactions, such as St. John's wort, are described in Section 4.4.2.1.

#### **4.4.3 Prohibited Therapy**

Use of the following concomitant therapies is prohibited as described below:

- Investigational therapy (other than protocol-mandated study treatment) is prohibited within 14 days prior to initiation of study treatment and during study treatment.
- Concomitant therapy intended for the treatment of cancer (including, but not limited to, chemotherapy, hormonal therapy, immunotherapy, radiotherapy, and herbal therapy) is prohibited for various time periods prior to starting study treatment, depending on the agent (see Section 4.1.2), and during study treatment, until disease progression is documented and the patient has discontinued study treatment, with the exception of palliative radiotherapy and local therapy under certain circumstances (see Section 4.4.1 for details).
- Quinidine or other anti-arrhythmic agents with a narrow therapeutic index
- Chronic use of strong CYP3A inhibitors or inducers, or sensitive CYP3A substrates with a narrow therapeutic window that are deemed not permissible by the Medical Monitor (refer to the guidance in Section 4.4.2)

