### **Cancer-Related Inclusion Criteria**

- Have a histologically confirmed diagnosis of ovarian (Part 1 only), breast (Part 1 only) or prostate cancer (Part 1 and Part 2)
- Disease must be either metastatic or locally advanced disease that cannot be treated with curative intent
- For patients with ovarian cancer (Part 1 only):
  - High-grade (2 or 3) serous or endometrioid *or clear cell* epithelial ovarian, fallopian tube, or primary peritoneal cancer (PPC)
    - If the tumor is of mixed histology,  $> 50\%$  of the primary tumor must be confirmed to be high-grade serous, endometrioid, *or clear cell*.
  - Must have received at least one prior platinum-based therapy and *may* have platinum-sensitive disease (i.e., documented radiologic disease progression  $\geq 6$  months following the last dose of the platinum treatment administered) *or platinum-resistant disease*
  - Have a CA-125 level that is  $> 2 \times \text{ULN}$
  - Must have measurable disease by RECIST v1.1
- For patients with breast cancer (Part 1 only): must be HER2-(ER/progesterone positive or negative)
  - ER/progesterone-positive patients must have received and progressed on at least one endocrine therapy (adjuvant or metastatic)
  - ER/progesterone-negative/HER2- (TNBC) patients must have received at least one prior line of chemotherapy for metastatic breast cancer
  - Must not have received more than two prior lines of chemotherapy for metastatic breast cancer
  - Must have measurable disease by RECIST v1.1
- For patients with prostate cancer:
  - Adenocarcinoma of the prostate without small cell or neuroendocrine features
  - Surgical or medical castration with testosterone  $< 50$  ng/dL (1.7 nM)

- Patients treated with luteinizing hormone-releasing hormone *analogs* must have initiated therapy at least 4 weeks prior to the first dose of study treatment and continue throughout the study treatment
- Progression of prostate cancer either via PSA progression (two rising PSA levels measured  $\geq 1$  week apart, with second result  $\geq 1$  ng/mL) or radiographic progression with or without PSA progression (see [Appendix 5](#) for guidance)
- Must have received at least one prior line of second-generation androgen receptor targeted therapy (e.g., abiraterone, enzalutamide, apalutamide)
- Patients with prostate cancer must have either measurable disease by RECIST v1.1 or bone lesions by bone scan, or both.

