#### **4.1.2 Exclusion Criteria**

Patients who meet any of the following criteria will be excluded from study entry:

- Pregnant or breastfeeding, or intending to become pregnant during the study or within 28 days after the final dose of ipatasertib or 6 months after the final dose of rucaparib

Women of childbearing potential must have a negative serum pregnancy test result within 3 days prior to initiation of study drug.

- Prior treatment with a PARP inhibitor, *AKT* inhibitor, or *PI3K* inhibitor
- Treatment with investigational therapy within 14 days prior to initiation of study drug
- Symptomatic and/or untreated CNS metastases

Patients with asymptomatic previously treated CNS metastases are eligible provided they have been clinically stable for at least 4 weeks.

Patients with leptomeningeal carcinomatosis will be excluded.

- Uncontrolled tumor-related pain

Symptomatic lesions (e.g., bone metastases or metastases causing nerve impingement) amenable to palliative radiotherapy should be treated prior to randomization. Patients should be recovered (e.g., to Grade 1 or resolved)

from the effects of radiation prior to study enrollment. There is no required minimum recovery period beyond the 7 days required for radiation therapy.

Asymptomatic metastatic lesions whose further growth would likely cause functional deficits or intractable pain (e.g., epidural metastasis that is not presently associated with spinal cord compression) should be considered for loco-regional therapy if appropriate prior to randomization.

- Non–study-related minor surgical procedures  $\leq 5$  days or major (invasive) surgical procedure  $\leq 14$  days prior to first dose of study treatment
  - Patient must be sufficiently recovered from surgery and stable, and wound healing must have occurred.
- Patients with active hepatitis C virus (HCV)
  - Patients positive for HCV antibody are eligible only if polymerase chain reaction (PCR) is negative for HCV RNA.
- Hepatitis B virus (HBV) infection (chronic or acute), defined as having a positive hepatitis B surface antigen (HBsAg) test or a positive quantitative HBV DNA test
  - If a patient has a negative HBsAg test and a positive total hepatitis B core antibody (HBcAb) test, a quantitative HBV DNA test must be performed.
  - Patients receiving anti-viral therapy for HBV are not eligible.
- Known HIV infection
- Illicit drug or alcohol abuse within 12 months prior to screening, in the investigator's judgment

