### **Ipatasertib-Specific Exclusion Criteria**

Patients who meet any of the following criteria specific to ipatasertib will be excluded from study entry:

- Type 1 or Type 2 diabetes mellitus requiring insulin at study entry
  - However, patients who are on a stable dose of oral diabetes medication  $\geq 4$  weeks prior to initiation of study treatment may be eligible for enrollment. Patients must meet the laboratory eligibility criteria for fasting blood glucose and HbA1c as outlined in the inclusion criteria.
- History of inflammatory bowel disease (e.g., Crohn disease and ulcerative colitis), active bowel inflammation (e.g., diverticulitis)
- Treatment with strong CYP3A inhibitors or strong CYP3A inducers within 4 weeks or five elimination half-lives of the inhibitors, whichever is longer, prior to initiation of study drug

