## 6.1 DETERMINATION OF SAMPLE SIZE

There is no formal hypothesis testing planned. The determination of sample size for each part is described below.

For Part 1 (Dose-Escalation Phase), approximately 24 patients are planned to be enrolled based on the dose-escalation rules.

For Part 2 (Dose-Expansion Phase), approximately 30 patients with advanced prostate cancer who have had at least one line of prior therapy with second-generation AR-receptor targeted agents (e.g., abiraterone, enzalutamide, apalutamide) are planned to be enrolled. No formal statistical hypothesis testing is planned. Instead, the analysis here is for hypothesis generation, and the emphasis is on estimations. To evaluate the primary endpoint of PSA response rate, the analyses will be based on patients enrolled in Part 2. [Table 16](#) shows estimated PSA response rate and its 95% CI based on the Clopper-Pearson method given various observed numbers of responders among the 30 patients. Thirty patients provide reasonably reliable estimates for hypothesis generation.

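### Section 4.4.3 refers to 4.1.2 for washout periods before study treatment, but 4.1.2 gives none for licensed cytotoxics, abiraterone or immunotherapy

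*Combined protocol and SAP*

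**What the plan says.** Section 4.4.3 covers anti-cancer treatment of every kind, naming chemotherapy, hormonal therapy and immunotherapy among others. It states that such treatment "is prohibited for various time periods prior to starting study treatment, depending on the agent (see Section 4.1.2"). The periods themselves are left to 4.1.2.

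Section 4.1.2, repeated in the synopsis, contains these limits on earlier treatment:

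- Investigational drugs: "Treatment with investigational therapy within 14 days prior to initiation of study drug".
- Radiotherapy, mentioned in passing under tumor-related pain: "There is no required minimum recovery period beyond the 7 days required for radiation therapy".
- Surgery: 5 days (minor) or 14 days (major).
- CYP3A agents: "Treatment with strong CYP3A inhibitors or strong CYP3A inducers within 4 weeks or five elimination half-lives of the inhibitors, whichever is longer". Section 4.4.2.1 describes lower ipatasertib exposure when it was "co-administered with enzalutamide, a strong CYP3A inducer", so this limit reaches enzalutamide.
- PARP, AKT and PI3K inhibitors: earlier use excludes the patient outright.

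Section 4.1.1 adds conditions that are not intervals. Earlier toxicity must have settled to Grade 1, with some exceptions. Blood counts and chemistry must meet thresholds on samples from the 28 days before the first dose, with no transfusion in that period and no G-CSF support for the neutrophil count. Patients on LHRH analogs "must have initiated therapy at least 4 weeks prior to the first dose of study treatment and continue throughout the study treatment". That is a rule about continuing a drug, not about stopping one.

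**The concern.** The protocol says that agent-dependent periods exist and where to find them, and for three large classes they are not there. The result is uneven: an investigational drug needs 14 days and radiotherapy 7, while a licensed taxane or abiraterone needs no stated time.

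The affected drugs are ordinary ones for this population. Every prostate patient must already have had a second-generation AR-targeted drug, with abiraterone among the examples, and every triple-negative breast cancer patient must have had chemotherapy (4.1.1). About 20 sites will enroll (9.4) and eligibility waivers are not allowed (9.2), so the written criteria are what sites have to work from.

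At stake are the safety of patients who start rucaparib soon after a marrow-toxic drug, and a clean reading of DLTs in Part 1. A smaller question is whether an earlier drug could affect the Part 2 PSA response rate.

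**Working it through.** **1. Tracing the reference.** I looked for an interval between the last earlier dose and the first study dose in 4.1.1, 4.1.2, the synopsis, 4.4 to 4.4.3 and Appendix 1.

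| Earlier treatment | Interval found |
|---|---|
| Investigational therapy | 14 days |
| Radiotherapy | 7 days |
| Strong CYP3A inhibitor or inducer (includes enzalutamide) | 4 weeks or five half-lives, whichever is longer |
| Licensed cytotoxic | none |
| Abiraterone, or another AR-targeted drug that is not a strong CYP3A inducer | none |
| Immunotherapy | none |

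**2. What still has to be met.** The qualifying laboratory values may be 28 days old, and nothing requires the blood count to be taken after the last dose of the earlier drug. In Part 1 the first study dose is ipatasertib on Day -7. Appendix 1 schedules hematology at screening and on Cycle 1 Day 1, with none on Day -7. Section 4.5.8 asks for blood counts to be available at the Day 1 visit, and Appendix 1 allows them to be up to 96 hours old. That review comes before the first rucaparib dose in both parts. It would show marrow suppression already present, but not suppression still to come. A delayed effect of a cytotoxic on counts is a general clinical assumption here; the documents do not quantify it.

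**3. Where toxicities overlap.** Section 5.1.2 lists anemia, thrombocytopenia, febrile neutropenia and decreased neutrophil count for rucaparib. Section 5.1.1 lists no cytopenia for ipatasertib. In Part 1, rucaparib starts on the evening of Cycle 1 Day 1, after 7 days of ipatasertib alone, so the run-in adds about a week. Part 2 has no run-in, so both drugs start together.

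**4. DLT attribution.** A dose level needs at least 6 patients with less than one-third having a DLT (3.1.1.1). 1/6 = 16.7% meets this; 2/6 = 33.3% does not. A single attribution can therefore decide a cohort. Table 15 treats an event as related unless there is evidence of another cause, and a recent cytotoxic is such evidence. The error could go either way: a cytopenia from the earlier drug counted as a DLT, or a true DLT put down to the earlier drug.

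**5. PSA response in Part 2.** Section 6.1 states: "To evaluate the primary endpoint of PSA response rate, the analyses will be based on patients enrolled in Part 2". For about 30 patients, one changed responder moves the rate by 1/30 = 3.3 points. The counts below are assumptions; the documents give no rate of exposure.

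- Starting point, also in Table 16: 6/30 = 20.0%, 95% Clopper-Pearson CI 7.71 to 38.57, width 38.57 - 7.71 = 30.9 points.
- One responder added: 7/30 = 23.3% (9.93 to 42.28).
- Two added: 8/30 = 26.7% (12.28 to 45.89).
- One lost: 5/30 = 16.7%.

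All four point estimates lie inside the interval for 6/30, and Part 2 has no test or threshold.

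**The case against.** The strongest reply is that 4.4.3 states a prohibition whose length is unspecified. It does not permit an early start, and a careful site would ask the Medical Monitor. This stands as far as it goes: a reader might infer that the protocol allows treatment days after a taxane, and the documents do not say so. But a prohibition of no stated length gives sites no common rule, and the eligibility list contains nothing that would exclude such a patient.

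A reader might also take 14 days from 4.4, which defines concomitant therapy as drugs used from 14 days before the first dose. That definition fixes what is reported and recorded for all medication. It is not a washout, and 4.4.3 itself points elsewhere for the periods.

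There are real safeguards: the count thresholds without transfusion or G-CSF support, the Day 1 laboratory review, the Part 1 run-in, the investigator's discretion in 4.1.2 to exclude a patient whose condition may confuse the results, and hematologic DLT definitions that require duration or complications. These reduce the harm, particularly in Part 1. None of them is an interval.

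The objection is strongest on PSA. A reader might infer that the response rate is inflated; the documents do not support that. Entry requires documented progression, so the exposed patients are mainly those with "radiographic progression with or without PSA progression" who had no PSA rise, or those treated again after progression. Central PSA is drawn on Cycle 1 Day 1 (4.5.7); if that is the baseline, any fall already achieved is in it. Stopping a partly active drug just before baseline could instead raise PSA and lower the rate. Section 6.4.1 asks for no minimum time or confirming value, but 3.1.3 defers to PCWG3, whose PSA response rule is not reproduced, so whether an early, unconfirmed fall counts cannot be settled here.

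Finally, a sponsor may reasonably be stricter with investigational drugs, so parity alone does not prove that 14 days is right. That is why it is proposed only as a minimum.

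**Conclusion.** The concern holds as a gap in the eligibility rules. Section 4.4.3 relies on periods that 4.1.2 does not contain for licensed cytotoxics, immunotherapy, and abiraterone or other AR-targeted drugs that are not strong CYP3A inducers. Enzalutamide and radiotherapy are covered and are not part of the gap.

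The consequences that matter are avoidable overlapping toxicity, chiefly of the marrow with rucaparib, and unclear DLT attribution in Part 1. How many patients would be affected is unknown, and the existing safeguards limit the harm. The case for acting rests on the small cohorts, where one attribution can decide a dose level, and on the low cost of a rule.

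The effect on the Part 2 PSA rate is secondary: possible, narrow, of unknown size and direction, and without bearing on any formal decision. The 3.3-point steps illustrate scale and do not estimate bias.

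**What to change.** Add one criterion to 4.1.2 and to the synopsis: at least 14 days from the last dose of any licensed systemic anti-cancer drug to the first dose of study treatment (Day -7 in Part 1, Cycle 1 Day 1 in Part 2). Exempt LHRH analogs continued under 4.1.1, and keep the longer CYP3A rule. The sponsor may set longer periods for particular agents, which would match what 4.4.3 promises more closely. The 14 days match the sponsor's own rule for investigational therapy and are not claimed to remove every residual effect. The cost is one line of text and a short wait for some patients.

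Optionally, report the Part 2 PSA response rate by time since last earlier therapy, with the window fixed in advance. The last-dose date should come from the cancer history (4.5.2; Appendix 1, footnote f), because the medication record reaches back only 14 days in 4.4 and 7 days in 4.5.2. Precision would fall somewhat. If the rate stayed at 20%, excluding 5 of 30 patients gives 5/25 (6.83 to 40.70, width 33.9 points) and excluding 10 gives 4/20 (5.73 to 43.66, width 37.9 points). Such a table could not separate one or two carried-over responders from chance, so it is descriptive only.

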#### **4.4.4 Prohibited Food**

Use of the following foods is prohibited as described below:

- Consumption of grapefruit juice, a potent CYP3A4 enzyme inhibitor, is prohibited during the study and for 10 days after the final dose of study treatment.

